9.3.2. Infant subjects

| | Description |
|---------------------|--|
| Analysis Set | |
| Exposed | Infants live-born to exposed maternal subjects, whose parents/LARs completed the informed consent process and signed the informed consent form |
| Full Analysis | All infant subjects in the Exposed set who have post-delivery/birth immunogenicity data. |
| Per Protocol | All infant subjects in the Full Analysis set minus those who (a) were born less than 4 weeks post- maternal subject vaccination and/ or (b) have protocol deviations that lead to exclusion. |
| Unsolicited Safety | All infants in the exposed set for whom unsolicited AEs /not having unsolicited AEs are reported |

9.3.3. Criteria for elimination from analysis

The Statistical Analysis Plan (SAP) will provide a complete list of criteria for elimination from per protocol analyses. Criteria may include, but are not limited to, those in Section [9.3.3.1](#) and [9.3.3.2](#).

9.3.3.1. Intercurrent medical conditions and concomitant medications/products/vaccines that may lead to elimination of a subject from per-protocol analyses**9.3.3.1.1. Maternal subjects**

- Any of the medications listed in Section [5.2.1.2](#) if administered up to Day 43 post-delivery (Visit 6).

CONFIDENTIAL209544 (RSV MAT-004)
Protocol Amendment 3 Final**9.3.3.1.2. Infant subjects**

- Systemic immunosuppressants or other immune-modifying drugs administered chronically (i.e. for more than 14 consecutive days) up to Day 43 post birth (Visit 2-NB), or Day 121 post birth (Visit 3-NB), or Day 181 post-birth (Visit 4-NB) depending on the relevant (visit-specific) sub-cohort for blood sampling.
 - For corticosteroids, this will mean prednisone or equivalent, ≥ 0.5 mg/kg/day.
 - Topical steroids are allowed.
 - Inhaled steroids are allowed if used in accordance with local labelling information (e.g. for budesonide).
- Immunoglobulins and/or any blood or plasma derivatives administered up to Day 43 post birth (Visit 2-NB), or Day 121 post birth (Visit 3-NB), or Day 181 post-birth (Visit 4-NB), depending on the infant's assigned sub-cohort for blood sampling.

9.3.3.1.3. Maternal and Infant subjects

- Diagnosis during the study with an immunological disorder or occurrence during the study of a condition (other than the study pregnancy) capable of altering immune response. For evaluation of immunogenicity endpoints in maternal and infant subjects, this includes RSV infection confirmed either locally or by GSK Biologicals during the specified analysis interval.
- Any investigational or non-registered product (drug or vaccine) other than the study vaccine/product administered during the specified analysis interval.

9.3.3.2. Other situations that may lead to elimination of a subject from per-protocol analyses

- Protocol violation(s) linked to the inclusion/ exclusion criteria, including age.
- Study vaccine/product not administered as specified by the protocol.
- Failure to comply with the post-vaccination immunogenicity blood sampling schedule at a given time-point ([Table 2](#), [Table 4](#)).

9.4. Statistical analyses**9.4.1. General considerations**

The statistical analysis plan (SAP) will be finalized before database lock and will include a more technical and detailed description of the statistical analyses to be performed. This section summarizes planned statistical analyses of primary and secondary endpoints.

The SAP describes how missing data will be handled during analyses.

CONFIDENTIAL209544 (RSV MAT-004)
Protocol Amendment 3 Final**9.4.1.1. Safety**

Safety analyses in **maternal subjects** will include summaries by study group and age category (18 - < 35 years of age; \geq 35 years of age; overall) of hematology and biochemistry results by grade and per time point, solicited administration site and systemic events, unsolicited AEs, MAEs, SAEs, , MA-RTIs,, RSV-associated MA-RTIs, AEs leading to study withdrawal, pregnancy outcomes and pregnancy related AESIs.

Safety analyses in **infant subjects** will include summaries by study group and gestational age at birth ($>$ 37 weeks or \leq 37 weeks) of neonatal AESIs, MAEs, SAEs, AEs leading to study withdrawal, and the occurrence of RSV-associated RTIs, LRTIs, severe LRTIs, very severe LRTIs and RSV-associated hospitalizations. Case definitions for RSV associated LRTIs are based on those described in [[Modjarrad, 2016](#)] and are described in Section [4.2.6](#).

All safety analyses will be performed on the Solicited Safety, Unsolicited Safety and Exposed sets.

9.4.1.2. Immunogenicity

The primary analysis will be based on the Per Protocol set for analysis of immunogenicity. If, in any study group and at any timepoint, the percentage of vaccinated subjects with serological results excluded from the Per Protocol set for analysis of immunogenicity is 5% or more, a second analysis based on the Full Analysis Set will be performed to complement the Per Protocol analysis.

9.4.2. Subject disposition

Number of screened, randomised, vaccinated and withdrawn maternal subjects in each group and overall will be described.

Number of infants enrolled and withdrawn (by group and subcohort, and overall) will be described. Additional analyses by country and/or by site may be performed.

CONFIDENTIAL

209544 (RSV MAT-004)
Protocol Amendment 3 Final

9.4.3. Primary endpoints

9.4.3.1. Safety

| Primary Safety Endpoints | | Statistical Analysis Methods |
|--------------------------|--|--|
| Maternal subjects | Occurrence of Solicited administration site and systemic events during a 7-day follow-up period after vaccination (i.e. the day of vaccination and 6 subsequent days). | 
The number and percentage with exact 95% CI of maternal subjects reporting each Solicited administration site event (any grade, each grade,) and solicited systemic event (any, each grade) during the 7-day (days 1 to 7) follow-up period after vaccination will be tabulated by maximum intensity per subject for each study vaccine group.
 
For fever during the 7-day follow-up period after vaccination, the number and percentage of maternal subjects reporting any fever (i.e., temperature ≥ 38 °C) and fever by half degree (°C) cumulative increments, any Grade 3 fevers, will be reported. In addition, the prevalence of any and Grade 3 fever will be presented graphically over time after vaccination.
 
The number and percentage of maternal subjects with at least one administration site AE (solicited and unsolicited), with at least one systemic AE (solicited and unsolicited) and with any AE during the 7-day follow-up period after vaccination will be tabulated with exact 95% confidence interval (CI) by group. The same computations will be done for Grade 3 solicited and unsolicited AEs, for any AEs considered related to vaccination, for any Grade 3 AEs considered related to vaccination and for any AEs resulting in a medically attended visit (i.e., MAEs).
 |
| | Occurrence of any protocol-specified hematological or biochemical laboratory abnormality at baseline (up to 15 days before vaccination) and Day 8 (Visit 2) | The number and percentage of subjects with hematology and biochemistry results outside central laboratory normal ranges will be tabulated to show Day 8 versus baseline. The maximum grading as described in [Sheffield, 2013] and in the SPM from Screening up to Day 8 will also be tabulated. |
| | Occurrence of unsolicited AEs that occur during a 30-day follow-up period after vaccination (i.e. the day of vaccination and 29 subsequent days). | 
The number and percentage of maternal subjects with unsolicited symptoms within 30 days after vaccination with exact 95% CIs will be tabulated by group and by Medical Dictionary for Regulatory Activities (MedDRA) preferred term.
 
Similar tabulations will be done for Grade 3 unsolicited symptoms, for any causally related unsolicited symptoms, for Grade 3 related unsolicited symptoms and for MAEs.
 
The number and percentage of maternal subjects with at least one administration site AE (solicited and unsolicited), with at least one systemic AE (solicited and unsolicited) and with any AE during the 30-day follow-up period after vaccination will be tabulated with exact 95% confidence interval (CI) by group. The same computations will be done for Grade 3 solicited and unsolicited AEs, for any AEs considered related to vaccination, for any Grade 3 AEs considered related to vaccination and for MAEs.
 |
| | Occurrence of serious adverse events (SAEs), AEs leading to study withdrawal, and medically attended AEs from Visit 1 | The number and percentage of maternal subjects with 
 • at least one SAE; • at least one MAE |

CONFIDENTIAL209544 (RSV MAT-004)
Protocol Amendment 3 Final

| Primary Safety Endpoints | | Statistical Analysis Methods |
|---------------------------------|--|--|
| | (Day 1) up to 6 weeks after delivery (Day 43 post-delivery, Visit 6). | from Visit 1 (Day 1) up to 6 weeks after delivery with exact 95% CIs will be tabulated by group and by Medical Dictionary for Regulatory Activities (MedDRA) preferred term. By-subject listings of SAEs, AEs leading to study withdrawal, and MAEs will be prepared (but will not be released until the final, unblinded analysis has been completed). |
| | Pregnancy outcomes from Day 1 (Visit 1) up to 6 weeks after delivery (Day 43 post-delivery, Visit 6). Outcomes are listed in Section 3. | The number and percentage of maternal subjects with each pregnancy outcome will be tabulated with its exact 95% CI by group. By subject listings of adverse pregnancy outcomes will be prepared but will not be released until the final, unblinded analysis has been completed. |
| | Pregnancy-related AESIs from Day 1 (Visit 1) up to 6 weeks after delivery (Day 43 post delivery; Visit 6). These events are listed in Section 3. | The number and percentage of maternal subjects with each pregnancy-related AESI will be tabulated with its exact 95% CI by group. By subject listings of pregnancy-related AESIs will be prepared but will not be released until the final, unblinded analysis has been completed. |
| Infant subjects | The occurrence of neonatal AESIs (reported up to 6 weeks after birth). These events are listed In Section 3. Occurrence of SAEs, AEs leading to study withdrawal and medically attended AEs from birth up to 6 weeks after birth. | The number and percentage of infant subjects with each neonatal AESI will be tabulated with its exact 95% CI by group. By-subject listings of neonatal AESIs will be prepared, but will not be released until the final, unblinded analysis has been completed. The number and percentage of infant subjects with 
 • at least one SAE; • at least one MAE from Visit 1 (Day 1) up to 6 weeks after delivery with exact 95% CIs will be tabulated by group and by Medical Dictionary for Regulatory Activities (MedDRA) preferred term. By-subject listings of SAEs, AEs leading to study withdrawal, and MAEs will be prepared (but will not be released until the final, unblinded analysis has been completed). |

CONFIDENTIAL209544 (RSV MAT-004)
Protocol Amendment 3 Final**9.4.3.2. Immunogenicity**

| Primary Immunogenicity Endpoints | | Statistical Analysis Methods |
|---------------------------------------|--|---|
| Maternal subjects | 
 RSVPreF3 IgG-specific antibody concentration, and Neutralizing antibody titers against RSV-A 
Measured on blood samples collected from vaccinated maternal subjects at Day 1 before vaccination (Visit 1), Day 31 (Visit 3), and at Delivery (Visit 5).
 | 
For each assay, at each timepoint and by study group and age category (18 - <35 years; ≥ 35 - years; overall):
 
 Antibody titres/concentrations will be displayed using reverse cumulative curves. Geometric Mean Titers (GMTs)/ Geometric Mean Concentrations(GMCs) will be tabulated with 95% CI and represented graphically. Individual post-vaccination versus pre-vaccination results will be plotted using scatter plots. Results of the control group will be used as a reference. Geometric mean of ratios of antibody titres/concentrations at each post-vaccination timepoint over pre-vaccination will be tabulated with 95% CI. The distribution of antibody titres/concentration will be tabulated Distribution of the fold increase of the antibody titres/concentrations (post- versus pre-vaccination) will be tabulated by pre-specified pre-vaccination titre category. 
Relationship between maternal RSVPreF3 IgG-specific antibody concentration and RSV-A neutralizing antibody at baseline, at day 31 and at delivery will be explored using scatter plots of individual values.
 
Between group evaluation of vaccine formulations in terms of RSVPreF3 IgG-specific antibody concentrations and Neutralizing antibody titers against RSV-A will be performed at Day31 and at Delivery using a mixed effect model on the \log_{10} transformation of the concentrations/titers, and including the pre-vaccination \log_{10} transformation of the concentrations/titers, the vaccine groups, gestational age at vaccination, and the interval between vaccination and delivery as covariates if needed.
 |
| Cord blood/ placental transfer | 
 RSVPreF3 IgG-specific antibody concentration, and Neutralizing antibody titers against RSV-A | 
For each assay, the following analysis will be performed by study group
 
 Antibody titres/concentrations will be displayed using reverse cumulative curves. Geometric Mean Titers (GMTs)/ Geometric Mean Concentrations(GMCs) will be tabulated with 95% CI and represented graphically. The distribution of RSV-A and RSVPreF3 IgG-specific antibody titres/concentration from cord blood will be tabulated For each assay, relationship between maternal antibody titers and infant antibody titers at the time of delivery will be evaluated graphically using scatter plots of individual results. |
| | 
 The ratio between cord blood and maternal RSVPreF3 IgG-specific antibody concentrations | 
 Geometric mean of placental transfer will be tabulated with 95% CI by study group. Percentage of infants with placental transfer ≥ 1 will be tabulated with exact 95 % CI by study group. |

CONFIDENTIAL209544 (RSV MAT-004)
Protocol Amendment 3 Final

| | Primary Immunogenicity Endpoints | Statistical Analysis Methods |
|--|---|---|
| | 
 All 3 endpoints measured on blood samples collected from maternal subjects at delivery and either cord blood, or (if cord blood cannot be collected) infant blood samples collected within 3 days after birth | 
Between group evaluation on vaccine formulations in terms of RSVPreF3 IgG-specific antibody concentrations / neutralizing antibody titers will be performed on cord blood at Delivery using a mixed effect model on the logarithm₁₀ transformation of the concentrations/titers, including the pre-vaccination logarithm₁₀ transformation of the concentrations/titers from maternal subjects, the vaccine groups, gestational age at vaccination, gestational age at birth (> 37 weeks; ≤ 37 weeks), and the interval between vaccination and delivery as covariates if appropriate.
 
In addition, if cord blood samples are missing in 20% or more of infants in a single study group, and if the data permit: RSV antibody concentrations/titers and persistence of RSV antibody concentrations/titers in infants through time will be evaluated separately in infants with cord blood samples and in infants from whom, instead, a blood sample was obtained within 3 days after birth.
 
The relationship between RSVPreF3 IgG-specific antibody concentration and RSV-A neutralizing antibody at delivery will be explored using scatter plots of individual values.
 |

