 - Placental abruption, placenta accreta/percreta/increta, chorioamnionitis or any abnormalities that in the opinion of Investigator can impair the maternal-fetal circulation
 - Polyhydramnios (defined as either a deepest vertical pocket of ≥ 8 cm or an amniotic fluid index of ≥ 24 cm on ultrasound examination) [Dashe, 2018]
 - Oligohydramnios (defined as a maximum vertical pocket shorter than 2 cm or amniotic fluid index ≤ 5 cm on the ultrasound examination) [Reddy, 2014]
 - Cervical suture in place
 - Preterm labour or history of preterm labour in the current pregnancy
 - Ongoing medical intervention to prevent preterm delivery or medical treatment for suspected preterm delivery

CONFIDENTIAL209544 (RSV MAT-004)
Protocol Amendment 3 Final

- Cholestasis (defined as unexplained pruritus and/or abnormal liver function tests and/or raised bile acids, based on investigator's clinical judgement) [[RCOG](#), 2011]
- Other pregnancy-related complications that in the Investigator's judgement would preclude participation of the subjects in an investigational vaccine trial or might pose risk to the subject due to participation in the study
- Significant (as per Investigator's judgement) structural abnormalities of the uterus or cervix.
- History of prior stillbirth or neonatal death
- History of preterm birth (< 37 weeks gestation)
- History of ≥ 2 spontaneous abortions.
- Known or suspected HBV or HCV infection, based on medical history and clinical presentation (no laboratory testing is required)
- Known or suspected infection during the current pregnancy with Toxoplasma, Parvovirus B19, Syphilis, Zika, Rubella, Varicella, CMV or primary genital Herpes Simplex, based on medical history and clinical presentation (no laboratory testing is required).
- Active infection with tuberculosis, based on medical history and clinical presentation (no lab testing is required).
- Known or suspected impairment of the immune system or autoimmune disorder (based on medical history and physical examination; no laboratory testing required).
- Lymphoproliferative disorder or malignancy within 5 years before vaccination (excluding effectively treated non-melanoma skin cancer).

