| | 
be randomly assigned to 1 of these 3 cohorts at the time of maternal randomization to intervention
 
For neutralizing antibody titers against RSV-B only: measured on the cord blood sample collected at delivery, or on a blood sample collected from the infant within 3 days after birth (if no cord blood sample can be obtained). (Note: RSV-A neutralizing antibody at birth is a primary immunogenicity objective).
 | 
logarithm₁₀ transformation of the concentrations/titers, including the pre-vaccination logarithm₁₀ transformation of the concentrations/titers from maternal subjects, the vaccine groups, gestational age at vaccination, gestational age at birth (> 37 weeks ; ≤ 37 weeks), and the interval between vaccination and delivery as covariates if appropriate and needed.
 
In addition, if cord blood samples are missing in 20% or more of infants in a single study group, and if the data permit: RSV antibody concentrations/titers and persistence of RSV antibody concentrations/titers in infants through time will be evaluated separately in infants with cord blood samples and in infants from whom, instead, a blood sample was obtained within 3 days after birth.
 
The relationship between RSVPreF3 IgG-specific antibody concentration and RSV-A neutralizing antibody, between RSV-A neutralizing antibody and RSV-B neutralizing antibody, and between RSV-B neutralizing antibody and RSVPreF3 IgG-specific antibody concentration at delivery will be explored using scatter plots of individual values.
 |

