9.4.5.2. Exploratory endpoints

Biomarker exploratory analyses and any other analysis (as applicable) will be described in a separate statistical analysis plan.

CONFIDENTIAL209544 (RSV MAT-004)
Protocol Amendment 3 Final**9.4.6. Other analyses****9.4.6.1. Demography and baseline characteristics**

These analyses will be performed on the Exposed set and on the Per protocol set for immunogenicity.

For all maternal subjects, demographic characteristics (e.g., age at vaccination (18 - <35; ≥ 35 years), gestational age at vaccination ($28^{0/7}$ - $31^{0/7}$, $31^{1/7}$ - $33^{6/7}$ weeks), geographic ancestry) will be summarized by group using descriptive statistics. The interval in days between maternal vaccination and delivery will be calculated and summarized by group using descriptive statistics. For their infants, demographic characteristics (e.g., gestational age at time of delivery (> 37 weeks; ≤ 37 weeks), sex, weight, length, head circumference, geographic ancestry, apgar score), and lifestyle characteristics (e.g., living environment, household composition, breastfeeding, passive smoking and extent of contact with children less than 6 years of age) will be summarised by group, and for each immunogenicity sub-cohort within each group, using descriptive statistics.

- Frequency tables will be generated for categorical variable such as geographic ancestry.
- Mean, median, standard deviation and range will be provided for continuous data such as age.

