Protocol Amendment 3 Final**Table 37 Non-reassuring fetal status**

Indicator of underlying event resulting in temporary or permanent oxygen deprivation to the fetus which may lead to fetal hypoxia and metabolic acidosis

| Levels of Diagnostic Certainty (Highest level (1) to lowest level of certainty) | |
|--|--|
| Level | Description |
| 1 | Category III fetal heart rate tracings detected via continuous cardiotocography as defined by NICHD Absent baseline fetal heart rate variability AND any of the following: recurrent late decelerations recurrent variable deceleration bradycardia (<110 bpm) OR Sinusoidal pattern AND Umbilical cord blood analysis consistent with metabolic acidosis (pH < 7.0 and Base deficit >12 mmol/L) |
| 2 | Category III fetal heart rate tracings detected via continuous cardiotocography as defined by NICHD Absent baseline fetal heart rate variability AND any of the following: recurrent late decelerations recurrent variable deceleration bradycardia (<110 bpm) OR Sinusoidal pattern |
| 3 | Fetal heart pattern detected via intermittent auscultation suggestive of fetal hypoxia Baseline Fetal Heart rate (FHR) <110 bpm or >160 bpm Presence of repetitive or prolonged (>3 min) decelerations More than 5 contractions in a 10 min period |

Reference: Gravett C, Eckert LO, Gravett MG, et al. Non-reassuring fetal status: Case definition & guidelines for data collection, analysis, and presentation of immunization safety data. *Vaccine*. 2016;34(49):6084-6092.

Table 38 Pathways to preterm birth

Premature preterm rupture of membranes; Preterm labor; Insufficient cervix (not applicable to this study, as women with insufficient cervix are ineligible); Provider-initiated preterm birth

Preterm = Birth at less than 37 gestation-completed weeks (less than 259 days).

| Levels of Diagnostic Certainty (Highest level (1) to lowest level of certainty) | |
|--|--|
| Preterm rupture of membranes | |
| Level | Description |
| All | Patient is determined to be preterm as defined above. On presentation, patient is determined to not be in preterm labor, having ≤4 contractions per hour documented clinically or on tocodynamometer, with <2 cm cervical dilation (greater than 4 contractions per hour would qualify the patient as having preterm labor) Fluid can be noted to be clear, blood-tinged, meconium-tinged (fetal stool), purulent-tinged (yellowish, suggesting infection) |

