| 1 | Live born infant AND Gestational age ≥22 and <28 weeks (GA Level of Certainty = 1) OR Birth weight ≥500 g but <1000 g AND Death of infant in first 28 days of life AND Medically-confirmed death |
| 2 | Live born infant AND Gestational age/size of newborn assessed as one or more of: Gestational age ≥22 and <28 weeks (GA Level of Certainty = 1 OR 2) Birth weight ≥500 g but <1000 g AND Death of infant in first 28 days of life AND Medically-confirmed death OR non-medically-confirmed death |

CONFIDENTIAL209544 (RSV MAT-004)
Protocol Amendment 3 Final

| Levels of Diagnostic Certainty (1 highest level to 4 lowest level of certainty) | |
|--|--|
| Neonatal death in an extremely preterm live birth (continued) | |
| Level | Description |
| 3 | Live born infant AND Gestational age ≥ 5 months but < 7 months according to neonate's parent (mother/father)/family member/delivery attendant (GA Level of Certainty = 2 OR 3) AND Death of infant in first 28 days of life AND Medically-confirmed death OR non-medically-confirmed death |
| Neonatal death in a preterm live birth (gestational age ≥ 28 to < 37 weeks) | |
| Level | Description |
| 1 | Live born infant AND Gestational age ≥ 28 and < 37 weeks (Level of Certainty = 1) OR Birth weight ≥ 1000 g but < 2500 g AND Death of infant in first 28 days of life AND Medically-confirmed death |
| 2 | Live born infant AND Gestational age/size of newborn assesses as one or more of: Gestational age ≥ 28 and < 37 weeks (GA Level of Certainty = 1 OR 2) Birth weight ≥ 1000 g but < 2500 g AND Death of infant in first 28 days of life AND Medically-confirmed death OR non-medically-confirmed death |
| 3 | (MAY apply to LMIC- or may be non-viable in LMIC) Live born infant AND Gestational age ≥ 7 months but < 9 months according to parent/family member/delivery attendant (GA Level of Certainty = 2 OR 3) AND Death of infant in first 28 days of life AND Medically-confirmed death OR non-medically-confirmed death |
| Neonatal death in a term live birth | |
| Level | Description |
| 1 | Live born infant AND Gestational age ≥ 37 weeks (GA Level of Certainty = 1) AND Birth weight > 2500 g OR Documented intra-uterine growth retardation if ≤ 2500 g AND Death of infant in first 28 days of life AND Medically-confirmed death |
| Neonatal death in a term live birth (continued) | |
| Level | Description |
| 2 | Live born infant AND Gestational age/size of newborn assesses as one or more of: Gestational age ≥ 37 weeks (GA Level of Certainty = 1 OR 2) |

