| | No medical record documentation, but reporting through either a non-medical observer (e.g. mother, father, community worker) or via standard census mechanisms (e.g. Demographic and Health Surveillance System) OR Collection of information from medical record review or billing codes. |
| 3 | No need for a level 3 per working group. |
| 4 | Not enough information to ascertain case of respiratory distress. |
| 5 | Not a case of respiratory distress in the neonate. |

Reference: Leigh R. Sweet, Cheryl Keech, Nicola P. Klein, et al. Respiratory distress in the neonate: Case definition & guidelines for data collection, analysis, and presentation of maternal immunization safety data. *Vaccine*. 2017; 35: 6506-6517.

Table 48 Preterm Birth

Birth in less than 37 gestation-completed weeks (less than 259 days).

| Prematurity and assessment of gestational age | |
|---|--|
| Level | Description |
| 1 | Certain last menstrual period date (LMP) LMP or intrauterine insemination (IUI) date or embryo transfer (ET) date with confirmatory 1st trimester scan ($\leq 13^{6/7}$ weeks). OR 1st trimester scan ($\leq 13^{6/7}$ weeks) |
| 2a | Certain LMP* with 2nd trimester scan (14 ^{0/7} weeks to 27 ^{6/7} weeks). Note: If LMP and U/S do not correlate, default to U/S GA assessment. OR Certain LMP* with 1st trimester physical examination. |
| 2b | Uncertain LMP with 2nd trimester scan (14 ^{0/7} weeks to 27 ^{6/7} weeks). |
| 3a | Certain LMP with 3rd trimester scan $\geq 28^{0/7}$ weeks OR Certain LMP with confirmatory 2nd trimester Fundal Height (FH) OR Certain LMP with birth weight OR Uncertain LMP with 1st trimester physical examination. |
| 3b | Uncertain LMP with FH. OR Uncertain LMP with newborn physical assessment. OR Uncertain LMP with Birth weight |
| * | Definitions of LMP, birth weight and physical assessment in referenced article. |

Reference: Quinn JA, Munoz FM, Gonik B, et al. Preterm birth: Case definition & guidelines for data collection, analysis, and presentation of immunization safety data. *Vaccine*. 2016;34(49):6047-6056.

Table 49 Failure to Thrive

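### The gestational-age-at-birth cut (>37 vs ≤37 weeks) does not match the protocol's own preterm/term boundary (<37 completed weeks), so some term infants fall in the lower group

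*Protocol*

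**What the plan says.** The cut at 37 weeks, with 37 itself in the lower group, appears in four sections of the protocol:

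- **9.4.1.1 (Safety):** infant analyses will include "summaries by study group and gestational age at birth", split at >37 or ≤37 weeks. They cover neonatal AESIs, MAEs, SAEs, withdrawals and RSV illness.
- **9.4.3.2 (primary cord-blood model):** "gestational age at birth (> 37 weeks; ≤ 37 weeks"), as a covariate if appropriate.
- **9.4.4.2 (secondary infant models):** "gestational age at birth (> 37 weeks ; ≤ 37 weeks"), as a covariate if appropriate and needed.
- **9.4.6.1 (Demography):** "gestational age at time of delivery (> 37 weeks; ≤ 37 weeks").

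The definitions elsewhere put 37 weeks with term births:

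- **Table 48 (preterm birth AESI):** "Birth in less than 37 gestation-completed weeks (less than 259 days").
- **Table 38 (pathways to preterm birth):** "Preterm = Birth at less than 37 gestation-completed weeks (less than 259 days").
- **Table 45 (neonatal death):** the term category starts at "Gestational age ≥ 37 weeks (GA Level of Certainty = 1"), and the preterm category runs from 28 to below 37 weeks.
- **Exclusion criteria (5.2.1.1):** "History of preterm birth (< 37 weeks gestation").
- **Table 49, footnote 4:** infants born at 37 weeks or later use a different growth chart from those born before 37 completed weeks.

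No section gives a reason for placing 37 weeks in the lower group.

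**The concern.** Thirty-seven weeks is the only preterm/term boundary the protocol uses, so a reader of the infant tables will take the lower group to be the preterm infants. As written, it is the preterm infants plus some term infants. Two things follow.

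- Event rates in the lower group of the 9.4.1.1 summaries describe a mixed group. For events that are more common in preterm infants, the rate would be diluted.
- Preterm birth is itself a neonatal AESI and part of a primary safety endpoint. The size of the ≤37 group in the demography and safety tables need not equal the number of infants with that AESI, and the report would have to explain the difference.

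The cut also carries no day notation, so two programmers could apply it differently.

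**Working it through.** **Boundary in days.** 37 × 7 = 259, which reproduces the figure in Tables 38 and 48. Preterm is day 258 or earlier; term is day 259 or later.

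**Classification.** Each gestational age from 196 to 300 days was classified by the preterm definition and by the ≤37 / >37 cut.

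| Reading of the cut | Term by definition but in the ≤37 group | Preterm but in the >37 group |
|---|---|---|
| Weeks + days | 37 0/7 only (day 259) | none |
| Whole completed weeks | 37 0/7 to 37 6/7 (days 259–265) | none |

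**Which reading is better supported.** The glossary expresses gestational age as completed weeks plus days. The gestational-age-at-vaccination groups (6.3.3 and 9.4.6.1) are 28 0/7–31 0/7 and 31 1/7–33 6/7, so the boundary day goes to the lower group and the next day to the upper. Read the same way, ≤37 / >37 moves only day 37 0/7.

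**Size.** Let p be the preterm share of births and s the share of births that are misplaced. The term share of the lower group is s / (s + p). The protocol gives p = 12% as a general-population rate (Table 19). It gives no value for s, so s is assumed. Counts are per 90 infants, matching the roughly 90 evaluable subjects per group in 9.2.2, so preterm infants number 90 × 0.12 = 10.8.

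| Reading | Assumed s | Term infants in lower group | Term share of lower group |
|---|---|---|---|
| Weeks + days | 1% | 0.9 | 0.01/0.13 = 8% |
| Weeks + days | 2% | 1.8 | 0.02/0.14 = 14% |
| Whole weeks | 5% | 4.5 | 0.05/0.17 = 29% |
| Whole weeks | 10% | 9.0 | 0.10/0.22 = 45% |

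**Sensitivity to p.** Women with a history of preterm birth, or with preterm labour in the current pregnancy, are excluded, so the trial's preterm rate may be below 12%. With an assumed p = 4%, the four shares become 0.01/0.05 = 20%, 0.02/0.06 = 33%, 0.05/0.09 = 56% and 0.10/0.14 = 71%. The number of misplaced infants does not change; only the preterm count beside them shrinks.

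**After the change.** With <259 vs ≥259 days, no gestational age from 196 to 300 days is classified differently from the preterm definition, under either reading.

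**The case against.** The strongest reply is that an adverse-event definition and an analysis grouping are different things and may use different cuts. The protocol never calls the ≤37 group preterm, never says its purpose is to show results in preterm infants, and never says its size should equal the preterm-birth AESI count. That is correct. A reader might infer that the protocol misclassifies term infants as preterm, but the text does not go that far: the two boundaries fail to match, with no reason given.

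A reader might also infer that the main results are distorted. They are not.

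- The endpoint tabulations of neonatal AESIs, SAEs, MAEs and RSV illness (9.4.3.1 and 9.4.4.1) are by study group. The preterm-birth AESI keeps its own definition there.
- Cord-blood and infant antibody displays are by study group only.
- In the models the factor is an optional covariate. The other listed covariates, gestational age at vaccination and the interval from vaccination to delivery, add up to gestational age at birth. If those are entered as continuous terms, moving a few infants across a binary cut changes little.
- The comparison between formulations is randomised, and 9.1 describes all analyses as descriptive.

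Finally, a reader might take it that close to half of the lower group would be term infants. That needs the whole-week reading, which the glossary and the vaccination groups do not favour, and the upper end of an assumed range.

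What remains is that four sections fix a cut that disagrees with every preterm or term definition in the same document, and that it does determine who is in the lower group of the 9.4.1.1 and 9.4.6.1 summaries.

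**Conclusion.** The mismatch is real and is shown by the protocol's own text. Infants born at 37 0/7 are term by Tables 38, 45 and 48 and by the wording of the exclusion criteria, yet fall in the lower group. On the better-supported weeks + days reading this is about 1 to 2 infants per 90, or 8% to 14% of the lower group, assuming 1% to 2% of births on that day and a 12% preterm rate. On the whole-week reading it would be 29% to 45%, assuming 5% to 10% of births in week 37. All these shares depend on assumed birth distributions and would be higher if the trial's preterm rate is lower. The consequence is confined to the gestational-age breakdown of the infant safety and demography summaries and to an optional model covariate. Primary by-group tabulations, AESI definitions, sample size and power stand as they are.

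**What to change.** In 9.4.1.1, 9.4.3.2, 9.4.4.2 and 9.4.6.1, state the cut as <37 weeks (<259 days) vs ≥37 weeks (≥259 days). Giving it in days removes the ambiguity between weeks + days and whole weeks, and makes the lower group coincide with the definition in Table 48. If 37 weeks is meant to sit in the lower group, say why, state that the group is not a preterm group, and write the boundary to the day.

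The cost is a wording change in four places and one derivation. Data collection, sample size and endpoint definitions do not change.
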